5.1.3.5 Timing of Dose Administration

Trial treatment of pembrolizumab may be administered up to 3 days before or after the scheduled Day 1 of each cycle due to administrative reasons (up to 5 days after randomization is permitted).

5.2 Rescue Medications & Supportive Care

5.2.1 Supportive Care Guidelines for Pembrolizumab

Subjects should receive appropriate supportive care measures as deemed necessary by the site investigator. Suggested supportive care measures for the management of adverse events with potential immunologic etiology are outlined below and in greater detail in. Where appropriate, these guidelines include the use of oral or intravenous treatment with corticosteroids as well as additional anti-inflammatory agents if symptoms do not improve with administration of corticosteroids. Note that several courses of steroid tapering may be necessary as symptoms may worsen when the steroid dose is decreased. For each disorder, attempts should be made to rule out other causes such as metastatic disease or bacterial or viral infection, which might require additional supportive care. The treatment guidelines are intended to be applied when the site investigator determines the events to be related to pembrolizumab.

Pneumonitis:

- For Grade 2 events, treat with systemic corticosteroids. When symptoms improve to Grade 1 or less, steroid taper should be started and continued over no less than 4 weeks.
- For Grade 3-4 events, immediately treat with intravenous steroids. Administer additional anti-inflammatory measures, as needed.
- Add prophylactic antibiotics for opportunistic infections in the case of prolonged steroid administration.

Diarrhea/Colitis:

Subjects should be carefully monitored for signs and symptoms of enterocolitis (such as diarrhea, abdominal pain, blood or mucus in stool, with or without fever) and of bowel perforation (such as peritoneal signs and ileus).

- All subjects who experience diarrhea/colitis should be advised to drink liberal quantities of clear fluids. If sufficient oral fluid intake is not feasible, fluid and electrolytes should be substituted via IV infusion. For Grade 2 or higher diarrhea, consider GI consultation and endoscopy to confirm or rule out colitis.
- For Grade 2 diarrhea/colitis that persists greater than 3 days, administer oral corticosteroids.
- For Grade 3 or 4 diarrhea/colitis that persists > 1 week, treat with intravenous steroids followed by high dose oral steroids.
- When symptoms improve to Grade 1 or less, steroid taper should be started and continued over no less than 4 weeks.

Type 1 diabetes mellitus (if new onset, including diabetic ketoacidosis [DKA]) or \geq Grade 3 Hyperglycemia, if associated with ketosis (ketonuria) or metabolic acidosis (DKA)

- For T1DM or Grade 3-4 Hyperglycemia
 - Insulin replacement therapy is recommended for Type I diabetes mellitus and for Grade 3-4 hyperglycemia associated with metabolic acidosis or ketonuria.
 - Evaluate subjects with serum glucose and a metabolic panel, urine ketones, glycosylated hemoglobin, and C-peptide.

Hypophysitis:

- For Grade 2 events, treat with corticosteroids. When symptoms improve to Grade 1 or less, steroid taper should be started and continued over no less than 4 weeks. Replacement of appropriate hormones may be required as the steroid dose is tapered.
- For Grade 3-4 events, treat with an initial dose of IV corticosteroids followed by oral corticosteroids. When symptoms improve to Grade 1 or less, steroid taper should be started and continued over no less than 4 weeks. Replacement of appropriate hormones may be required as the steroid dose is tapered.

Hyperthyroidism or Hypothyroidism:

Thyroid disorders can occur at any time during treatment. Monitor subjects for changes in thyroid function (at the start of treatment, periodically during treatment, and as indicated based on clinical evaluation) and for clinical signs and symptoms of thyroid disorders.

- Grade 2 hyperthyroidism events (and Grade 2-4 hypothyroidism):
 - In hyperthyroidism, non-selective beta-blockers (e.g. propranolol) are suggested as initial therapy.
 - In hypothyroidism, thyroid hormone replacement therapy, with levothyroxine or liothyroinine, is indicated per standard of care.
- Grade 3-4 hyperthyroidism
 - Treat with an initial dose of IV corticosteroid followed by oral corticosteroids. When symptoms improve to Grade 1 or less, steroid taper should be started and continued over no less than 4 weeks. Replacement of appropriate hormones may be required as the steroid dose is tapered.

Hepatic:

- For Grade 2 events, monitor liver function tests more frequently until returned to baseline values (consider weekly).
 - Treat with IV or oral corticosteroids
- For Grade 3-4 events, treat with intravenous corticosteroids for 24 to 48 hours.
- When symptoms improve to Grade 1 or less, a steroid taper should be started and continued over no less than 4 weeks.

Renal Failure or Nephritis:

- For Grade 2 events, treat with corticosteroids.
- For Grade 3-4 events, treat with systemic corticosteroids.
- When symptoms improve to Grade 1 or less, steroid taper should be started and continued over no less than 4 weeks.

Management of Infusion Reactions: Signs and symptoms usually develop during or shortly after drug infusion and generally resolve completely within 24 hours of completion of infusion. Appropriate resuscitation equipment should be available in the room and a physician readily available during the period of drug administration.

Table 5 shows treatment guidelines for subjects who experience an infusion reaction associated with administration of pembrolizumab (MK-3475).

Table 5 Infusion Reaction Treatment Guidelines

NCI CTCAE Grade	Treatment	Premedication at subsequent dosing
Grade 1 Mild reaction; infusion interruption not indicated; intervention not indicated	Increase monitoring of vital signs as medically indicated until the subject is deemed medically stable in the opinion of the site investigator.	None
Grade 2 Requires infusion interruption but responds promptly to symptomatic treatment (e.g., antihistamines, NSAIDS, narcotics, IV fluids); prophylactic medications indicated for <=24 hrs	
Stop Infusion and monitor symptoms.
 
Additional appropriate medical therapy may include but is not limited to:
 
IV fluids Antihistamines NSAIDS Acetaminophen Narcotics
 
Increase monitoring of vital signs as medically indicated until the subject is deemed medically stable in the opinion of the site investigator.
 
If symptoms resolve within one hour of stopping drug infusion, the infusion may be restarted at 50% of the original infusion rate (e.g., from 100 mL/hr to 50 mL/hr). Otherwise dosing will be held until symptoms resolve and the subject should be premedicated for the next scheduled dose.
 
Subjects who develop Grade 2 toxicity despite adequate premedication should be permanently discontinued from further trial treatment administration.
	
Subject may be premedicated 1.5h (\pm 30 minutes) prior to infusion of pembrolizumab with:
 
Diphenhydramine 50 mg po (or equivalent dose of antihistamine).
 
Acetaminophen 500-1000 mg po (or equivalent dose of antipyretic).

Grades 3 or 4 Grade 3: Prolonged (i.e., not rapidly responsive to symptomatic medication and/or brief interruption of infusion); recurrence of symptoms following initial improvement; hospitalization indicated for other clinical sequelae (e.g., renal impairment, pulmonary infiltrates)	
Stop Infusion.
 
Additional appropriate medical therapy may include but is not limited to:
 
IV fluids Antihistamines NSAIDS Acetaminophen Narcotics Oxygen Pressors Corticosteroids Epinephrine
	No subsequent dosing

NCI CTCAE Grade	Treatment	Premedication at subsequent dosing
Grade 4: Life-threatening; pressor or ventilatory support indicated	
Increase monitoring of vital signs as medically indicated until the subject is deemed medically stable in the opinion of the site investigator.
 
Hospitalization may be indicated.
 
Subject is permanently discontinued from further trial treatment administration.
	

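### Section 5.2.1 has steroids for pembrolizumab-related Grade 3-4 diarrhea/colitis wait longer (more than 1 week) than for Grade 2 (more than 3 days), and Table 4 leaves Grade 3 timing ambiguous

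*Combined protocol and SAP*

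**What the plan says.** Section 5.2.1 gives two steroid triggers for diarrhea/colitis, both conditional on persistence.

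- Grade 2: "For Grade 2 diarrhea/colitis that persists greater than 3 days, administer oral corticosteroids".
- Grade 3-4: "For Grade 3 or 4 diarrhea/colitis that persists > 1 week, treat with intravenous steroids followed by high dose oral steroids".

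The introduction to 5.2.1 limits the scope: "The treatment guidelines are intended to be applied when the site investigator determines the events to be related to pembrolizumab". It also calls the measures suggested and leaves their need to the site investigator.

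Table 4 in section 5.1.3.4 covers the same toxicity. For Grade 2 or 3 it withholds pembrolizumab and gives corticosteroids at an initial 1-2 mg/kg prednisone equivalent, then a taper. It states no waiting period, start time or route. For Grade 4 it permanently discontinues the drug; the steroid cell beside Grade 4 is blank in the text available to me.

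Section 5.1.3.1 leaves the final decision on supportive therapy to the site investigator and/or the primary physician.

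**The concern.** Within one short list, the milder event is treated sooner than the severe one, and the protocol gives no reason for that order. Diagnostic caution is not an obvious explanation: the guidance applies once the investigator has attributed the event to the drug, and the instruction to rule out other causes covers every disorder in the section, so it does not justify a longer wait for the worse grade.

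The protocol itself treats the toxicity as serious. Table 4 and 5.2.1 both ask sites to watch for bowel perforation, and section 10.1.6 lists colitis among important immune-mediated risks, some of them fatal. A site among the up to 30 centers that took the bullet literally could hold steroids for more than a week in a severe event it had already attributed to pembrolizumab.

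**Working it through.** **1. The two triggers in 5.2.1.** Grade 2: more than 3 days, so day 4. Grade 3-4: more than 1 week, so day 8. Difference: 8 − 4 = 4 days later for the more severe event. No other bullet under diarrhea/colitis gives steroids earlier for Grade 3-4.

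**2. The rest of 5.2.1.** Six toxicities carry a Grade 3-4 steroid instruction:

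| Toxicity | Grade 3-4 instruction | Persistence condition |
|---|---|---|
| Pneumonitis | "For Grade 3-4 events, immediately treat with intravenous steroids" | None |
| Diarrhea/colitis | intravenous, then high-dose oral | More than 1 week |
| Hypophysitis | "For Grade 3-4 events, treat with an initial dose of IV corticosteroids followed by oral corticosteroids" | None |
| Hyperthyroidism | "Treat with an initial dose of IV corticosteroid followed by oral corticosteroids" | None |
| Hepatic | "For Grade 3-4 events, treat with intravenous corticosteroids for 24 to 48 hours" (a duration, not a wait) | None |
| Renal | "For Grade 3-4 events, treat with systemic corticosteroids" | None |

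Only diarrhea/colitis has a persistence condition. Only pneumonitis gives an explicit start time; the other four are silent on it.

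**3. 5.2.1 against Table 4.**

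| Grade | 5.2.1 | Table 4 |
|---|---|---|
| 2 | oral, after more than 3 days | 1-2 mg/kg, no stated wait |
| 3 | intravenous then oral, after more than 1 week | 1-2 mg/kg, no stated wait |
| 4 | as Grade 3 | steroid cell blank in the extracted text |

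For Grade 3, at least two readings are open. Table 4 may start steroids, with 5.2.1 escalating to the intravenous route if the event persists; then there is no wait. Or Table 4 may give the dose and 5.2.1 the timing; then steroids wait more than a week. The visible text does not choose between them.

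**4. How many events the wording could touch.** Inputs: 108 subjects randomized 1:1 (section 12.1), so 108/2 = 54 on pembrolizumab; drug-related Grade 3-4 diarrhea in 1 of 135 melanoma patients (section 1.7, Table 1). The assumption is that this rate applies here.

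- Rate p = 1/135 = 0.74%; exact (Clopper-Pearson) 95% CI 0.02% to 4.06%.
- Expected events = n × p; chance of at least one = 1 − (1 − p)^n. Ranges use the CI limits.

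| Exposed to pembrolizumab | n | Expected (range) | Chance of at least one (range) |
|---|---|---|---|
| Randomized arm only | 54 | 0.4 (0.01 to 2.2) | 33% (1% to 89%) |
| Plus half of placebo arm crossing over | 81 | 0.6 (0.02 to 3.3) | 45% (2% to 97%) |
| Plus all of placebo arm (ceiling) | 108 | 0.8 (0.02 to 4.4) | 55% (2% to 99%) |

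Cross-over uptake is unknown, because section 7.3.3 requires the section 3 eligibility still to be met.

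For Grade 2, Table 1 gives only Grades 1 and 2 combined: 27 − 1 = 26 of 135 = 19.3% (exact 95% CI 13.0% to 26.9%). That is 54 × 26/135 = 10.4 Grade 1-2 events in the randomized arm (range 7.0 to 14.5), of which Grade 2 is an unknown part.

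**The case against.** The strongest reply is that the Grade 3-4 bullet is an escalation step. Table 4 already gives steroids for Grade 2-3; 5.2.1 would then add intravenous and high-dose oral treatment for events that do not settle. On that reading Grade 3 has no delay. This stands as a competing reading, but 5.2.1 does not describe itself as escalation and its Grade 2 bullet reads as a first steroid step. A reader might infer the opposite extreme, that the week's wait is the operative rule or that the protocol tells sites to withhold steroids. The documents do not support that either: nothing forbids earlier steroids.

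Second, the guidance is suggested, the clinician decides, and several safeguards carry no wait: monitoring for enterocolitis and perforation, fluids, consideration of GI consultation and endoscopy, and withholding or stopping pembrolizumab. These reduce the likely harm. They do not correct the order printed in 5.2.1.

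Third, different organ toxicities need not share a trigger. That is fair. A reader might take the comparison within 5.2.1 to show that all other severe toxicities require immediate steroids; only pneumonitis says so. The comparison is supporting evidence only, and the point rests on the order of grades within diarrhea/colitis.

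Fourth, a timing or precedence rule may have been lost when the text was extracted: the general instructions row of Table 4 is empty and a cross-reference in the 5.2.1 introduction is cut off. The blank Grade 4 steroid cell is probably merged with the one above, since pneumonitis and nephritis show the same pattern. None of these gaps is counted as a fault here. A precedence rule could settle the Table 4 question but would leave the 5.2.1 inversion in print.

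**Conclusion.** The point holds as a limited patient-safety inconsistency. Section 5.2.1 inverts the steroid trigger by severity, with a 4-day difference. Set beside Table 4, it leaves Grade 3 timing ambiguous at best and delayed at worst. No conflict with Table 4 is claimed for Grade 4, because its steroid cell cannot be read with certainty.

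The scale is small: about 0.4 expected Grade 3-4 events in the randomized pembrolizumab arm. This rests on a single melanoma event, on the assumption that the rate carries over to this population, and on a diarrhea rate standing in for diarrhea/colitis, as Table 1 has no colitis row. A reader might take the counts as subjects harmed. They are events to which the wording applies; the documents give no data on how long such events last or how long clinicians would wait.

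Sample size, primary endpoint and analysis are unaffected. The change should be made because it is nearly free and corrects a stated safety instruction; confidence is medium, given the escalation reading.

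**What to change.** 1. In the Grade 3-4 diarrhea/colitis bullet of 5.2.1, delete the persistence clause (*that persists > 1 week*) and leave the rest of the treatment instruction as it is.
2. Add that for Grade 3 the initial dose follows Table 4. Before making the same cross-reference for Grade 4, confirm in the source file that the Table 4 steroid cell covers Grade 4.
3. If escalation of persistent events was intended, say so in a separate bullet that follows the initial steroid step.
4. For Grade 2, align the two places: either put the 3-day trigger in Table 4 as well or remove it from 5.2.1. The documents do not settle which.
5. Check the source file for a precedence statement in the general instructions row of Table 4 and at the cut cross-reference in 5.2.1.

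The cost is one clause deleted, one cross-reference added and one decision on Grade 2. Data collection, sample size and analysis do not change.

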5.3 Diet/Activity/Other Considerations

5.3.1 Diet

Subjects should maintain a normal diet unless modifications are required to manage an AE such as diarrhea, nausea or vomiting.

5.3.2 Contraception

Pembrolizumab may have adverse effects on a fetus in utero. Furthermore, it is not known if pembrolizumab has transient adverse effects on the composition of sperm. Therefore, non-pregnant, non-breast-feeding women may only be enrolled if they are willing to use an adequate form of contraception or are considered highly unlikely to conceive. Highly unlikely to conceive is defined as 1) surgically sterilized, or 2) postmenopausal (a woman who is ≥ 45 years of age and has not had menses for greater than 1 year will be considered postmenopausal), or 3) not heterosexually active for the duration of the study. The two birth control methods can be either two barrier methods or a barrier method plus a hormonal method to prevent pregnancy. Subjects should start using birth control from study Visit 1 throughout the study period up to 120 days after the last dose of study therapy.

The following are considered adequate barrier methods of contraception: diaphragm, condom (by the partner), copper intrauterine device, sponge, or spermicide as per local regulations or guidelines. Appropriate hormonal contraceptives will include any registered and marketed contraceptive agent that contains an estrogen and/or a progestational agent (including oral, subcutaneous, intrauterine, or intramuscular agents).

Subjects should be informed that taking the study medication may involve unknown risks to the fetus (unborn baby) if pregnancy were to occur during the study. In order to participate in the study they must adhere to the contraception requirement (described above) for the duration of the study and during the follow-up period. If there is any question that a subject will not reliably comply with the requirements for contraception, that subject should not be entered into the study.

5.3.3 Use in Pregnancy

If a subject inadvertently becomes pregnant while on treatment with pembrolizumab, the subject will immediately be removed from the study. The site will contact the subject at least monthly and document the subject's status until the pregnancy has been completed or terminated. The site investigator will make every effort to obtain permission to follow the outcome of the pregnancy and report the condition of the fetus or newborn to HCRN. If a male subject impregnates his female partner the study personnel at the site must be informed immediately and the pregnancy reported to HCRN and followed as described above.

5.3.4 Use in Nursing Women

It is unknown whether pembrolizumab is excreted in human milk. Since many drugs are excreted in human milk, and because of the potential for serious adverse reactions in the nursing infant, subjects who are breast-feeding are not eligible for enrollment.

6 TREATMENT DISCONTINUATION

6.1 Reasons for Discontinuing Protocol Therapy

A subject will be discontinued from protocol therapy under the following circumstances:

- If there is evidence of progressive disease. However, subjects randomized to placebo will be eligible to cross over to pembrolizumab treatment at the time of progression.
- If the site investigator thinks a change of therapy would be in the best interest of the subject.
- If the drug(s) exhibit(s) an unacceptable adverse event.
- If a subject becomes pregnant or is unwilling to use appropriate birth control techniques as outlined in the inclusion criteria.
- If there is a treatment interruption for greater than 12 weeks due to treatment related adverse event.
- Subjects can stop participating at any time. However, if they decide to stop participating in the study, subjects will continue to be followed for disease progression and survival.
- Twenty-four months of uninterrupted protocol therapy and no evidence of progressive disease.

6.2 Reasons for Withdrawal from Study

- Subject withdraws consent for participation
- Termination of the study
- Lost to follow-up
- Death

7 STUDY SCHEDULE OF EVENTS

	Screening		On Treatment Cycle = 3 weeks (up to 24 months)	Progression/Unblinding EOT ¹⁵	Cross-over to pembrolizumab	Follow-up
	-28 days	-14 days				
REQUIRED ASSESSMENTS						
Eligibility evaluation (review of inclusion and exclusion criteria) ¹	X	X				
Medical history		X				
Physical examination		X				
Vitals and ECOG performance status ²		X				
Charlson Comorbidity Index		X				
Smoking History Questionnaire ³		X				
AEs & concomitant medications		X				
LABORATORY ASSESSMENTS						
CMP ⁴		X				
CBC ⁴		X				
PT/INR and aPTT ⁵		X				
Thyroid Function (TSH, T3 and T4) ⁶		X				
Serum pregnancy test ⁷		X ⁷				
DISEASE ASSESSMENT						
CT or MRI of chest, abdomen, and pelvis	X ¹²					
TREATMENT EXPOSURE						
pembrolizumab or placebo (IV)						
CORRELATIVE STUDIES						
Archival tumor tissue for research ⁸	X					
Tumor Biopsy if archival tissue not available ⁸	X					
Tumor Biopsy for sub-study analysis ⁸	X					
Blood samples for research ⁹						
FOLLOW-UP						
For progression, start date of additional cancer treatment, and survival ¹⁴						X ¹⁴

RANDOMIZATION

1. Subjects should undergo informed consent prior to any research specific testing being performed. Subjects randomized to Arm A (placebo) who discontinue treatment due to progression or unacceptable toxicity will be eligible to cross over to pembrolizumab provided eligibility outlined in section 3 is met. (**NOTE:** inclusion criteria #6 regarding initiation of study treatment within 2 to 6 weeks of completing first line chemotherapy only applies to initial randomization to placebo). Cross over treatment should be initiated within 4 weeks of confirming eligibility. Subjects initiating treatment with pembrolizumab from placebo will follow the same schedule outlined in the calendar above and receive up to 24 months of treatment unless progression or unacceptable toxicity is experienced.
2. Vital signs (blood pressure, weight [kg] and height [cm] SCREENING ONLY and ECOG performance status.
3. Smoking Questionnaire in Appendix A
4. CMP includes: serum chemistries (creatinine, glucose, total protein, blood urea nitrogen [BUN], total carbon dioxide [CO₂], albumin, total bilirubin, alkaline phosphatase, and aspartate transaminase [AST] and alanine transaminase [ALT]) and electrolytes (total calcium, chloride, potassium, sodium). CBC includes: platelets, ANC & HGB.
5. Repeat PT/INR and aPTT tests for subjects being screened for eligibility to cross over to pembrolizumab.
6. TSH, T3 and T4 tests are done on Day 1 of even numbered cycles only (i.e., Cycle 2, 4, 6, etc.). For T3 and T4, free versus total is at the site investigator's discretion
7. Obtain a negative serum pregnancy test for females of childbearing potential within three days of registration for protocol therapy.
8. Request from all subjects, **archived tumor tissue** (primary or metastatic based on availability) for research. If archival tissue is unavailable, obtain an excisional or percutaneous **core biopsy** (only) for research. If no sites are amendable to biopsy, enrollment must be discussed with the sponsor-investigator on a case by case basis. **NOTE for biopsy for sub-study analysis:** If the subject has archived primary tissue available and has agreed to the optional exploratory sub-study analysis, collect archived **primary** tumor tissue at baseline, **and obtain** an excisional or percutaneous core biopsy (only) for research.
9. Blood samples for research will be collected prior to treatment on Cycle 1 Day 1, Cycle 4 Day 1, and at Progression (if subject's disease progressed) or End of Treatment (if for a reason other than progression). Samples will be obtained during the randomized portion of the trial and at these same time points for subjects who cross over from placebo to unblinded treatment with pembrolizumab. Subjects crossing over from placebo to unblinded treatment with pembrolizumab will have their initial progression samples count as their cross over Cycle 1 Day 1 samples. Blood samples are not to be shipped so that they are received on a weekend or holiday. Samples leftover after initial protocol testing is complete may be stored for unspecified future cancer related research. Consent will be obtained from subjects.
10. Cycle 1 Day 1 only, required tests do not need to be repeated if done within seven days prior.
11. Restaging CT or MRI of the chest, abdomen, and pelvis is performed after every four cycles of treatment (i.e., approximately every 12 weeks). Make every effort to perform the same imaging modality throughout the study. After the first documentation of progression per RECIST 1.1, if the subject is clinically stable, confirmatory scans should be performed 4-6 weeks later (see Section 7.6 for details).
12. Repeat imaging tests if it has been > 28 days since the last radiological assessment.
13. Subjects who discontinue treatment without evidence of progression will be followed with imaging studies performed every three months (\pm 7 days), or until new anticancer treatment is initiated. Make every effort to perform the same imaging modality throughout the follow up period.
14. After the EOT visit, make every possible attempt to contact the subject or family to information on start date of additional anticancer treatment and survival, every three months (\pm 7 days) during the first two years, every six months (\pm 7 days) during years 3-5, and annually (\pm 2 weeks) thereafter.

15. Treatment will be discontinued if evidence of disease progression, unacceptable toxicity, subject withdraws or after 24 months, whichever comes first. Please see Section 7.3.2 for unblinding and Section 7.3.3 for cross over information.

Table 6 Schedule for correlative blood sample collections*

Time point	Correlative blood samples
Pre-Treatment Cycle 1 Day 1	1 red top tube (10 ml total) 1 Tempus tubes (3 ml total) 6 ACD tubes (51 ml total)
Pre-Treatment Cycle 4 Day 1	1 red top tube (10 ml total) 1 Tempus tubes (3 ml total) 6 ACD tubes (51 ml total)
Time of progression**	1 red top tube (10 ml total) 1 Tempus tubes (3 ml total) 6 ACD tubes (51 ml total)
End of treatment***	1 red top tube (10 ml total) 1 Tempus tubes (3 ml total) 6 ACD tubes (51 ml total)
Cross-over Cycle 1 Day 1**	1 red top tube (10 ml total) 1 Tempus tubes (3 ml total) 6 ACD tubes (51 ml total)
Cross-over Cycle 4 Day 1	1 red top tube (10 ml total) 1 Tempus tubes (3 ml total) 6 ACD tubes (51 ml total)
Cross-over Time of progression	1 red top tube (10 ml total) 1 Tempus tubes (3 ml total) 6 ACD tubes (51 ml total)
End of treatment***	1 red top tube (10 ml total) 1 Tempus tubes (3 ml total) 6 ACD tubes (51 ml total)

*Samples will be obtained during the randomized portion of the trial and at these same time points for subjects who cross over from placebo to unblinded treatment with pembrolizumab

**Subjects crossing over from placebo to unblinded treatment with pembrolizumab will have their initial progression samples count as their cross over Cycle 1 Day 1 samples

***Subjects discontinuing treatment for reasons other than progression will have correlative samples drawn at the end of treatment visit.

